The responsibility of the DMC is to evaluate safety data during the course of the trial and to advise Medtronic about the continuing safety of the trial, to ensure the wellbeing of the current participants and those yet to be enrolled as well as the continuing validity and scientific merit of the trial.

Medtronic will provide listings of all Adverse Events and Device Deficiencies to the Independent Medical Monitor to evaluate safety of the study device. All events, including any device related events will be reviewed on a case by case base by the Independent Medical Monitor. In case of a safety concern the Independent Medical Monitor can trigger a DMC meeting.

Trial data will be reviewed on a periodic basis as defined in the DMC Charter.

Based on the safety data, the DMC may recommend that Medtronic modify or stop the trial. DMC composition, duties, procedures, deliberation rules are detailed and documented in the DMC Charter.

F.6.7 Emergency contact details in case of serious AEs

In case of an immediately reportable Adverse Event the investigators can contact the Medtronic Study Manager. Contact details of Medtronic Study Management are given in the Investigational Site File.

In case the investigator requires information in a medical emergency situation the investigator can contact the Medical Expert. Contact details of Medical Expert are given in the Investigational Site File.

F.7 Subject accountability

Every subject should be encouraged to remain in the study until they have completed the required follow up per the study protocol.

If a subject is withdrawn from the clinical study, the reason for withdrawal shall be recorded on the appropriate eCRF and in the subject's hospital record. If discontinuation is because of safety or lack of effectiveness, the subject shall be asked to be followed for collecting safety data outside the clinical study. Subjects will not be replaced in case of premature study discontinuation.

F.7.1 Criteria and procedures for exit from study

The Study Exit Form should be completed at the time a subject is exited from the study. A subject will be considered to have exited from the study for any of the following reasons:

- Subject completes follow-ups required by the investigational plan.
- Subject dies.
- Subject requests to be withdrawn.
- Investigator requests that subject be withdrawn to protect the welfare of the subject.
- Subject is lost to follow-up.
- Other (specify).

F.7.2 Study Withdrawal

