Subjects may withdraw from the study at any time and for any reason. If a subject decides to withdraw from the study, the investigator will document the reason for withdrawal and indicate any relationship of the withdrawal to the study or products being investigated in the subject's hospital record in the subject's file. If discontinuation is because of safety or lack of effectiveness, the subject shall be asked to be followed for collecting safety data outside the clinical study as further described in section F.7.6. In addition, subject withdrawal will be documented on Study Exit eCRF.

If the subject is unable to be followed, the investigator has to notify the sponsor in a timely manner.

F.7.3 Missed follow-up

A missed follow-up visit should be documented by the investigator and reported in the eCRF, including the reason. If the date the subject is last known to be alive is obtained, this should be recorded on the Follow-up visit eCRF and the method of obtaining this date should be documented in the medical record.

F.7.4 Lost-to-follow-up

A subject may be considered lost to follow-up once the investigator and/or research staff has made three documented attempts to contact the subject. The third attempt should be made by certified mail to the subject.

F.7.5 Medical care after study exit

After study exit the subjects will be followed as per routine standard of care by the investigational site or a treating physician.

F.8 Study deviations and CIP changes

A protocol deviation is defined as an event where the clinical investigator or site personnel did not conduct the study according to the clinical investigational plan, applicable laws or regulations, or the Investigator Agreement. Every attempt must be made to avoid deviations. All deviations are recorded on a Protocol Deviation Case Report Form. United States regulations (21 CFR 812.140) require that investigators maintain accurate, complete, and current records relating to the clinical study. This includes documents showing the dates and reasons for each deviation from the clinical investigational plan. Depending on the nature of the protocol deviation, expedited reporting and prior approval from Medtronic may be required. All protocol deviations must be reported to the Institutional Review Board (IRB) in accordance with IRB policies and/or local laws. All deviations will be summarized and reported in regular progress reports to the FDA.

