m = No. of Subjects Who Had MDE(s)	No. of subjects who had at least one MDE with onset day from Day 0 to Day 30, inclusive.	No. of subjects who had at least one MDE with onset day from Day 0 to Day 183, inclusive.	No. of subjects who had at least one MDE with onset day from Day 0 to Day 365, inclusive.
k = No. of Subjects Who Had No MDE	No. of subjects who have been in study for at least 1 day and without an MDE.	No. of subjects who have been in study for at least 91 days and without an MDE.	No. of subjects who have been in study for at least 305 days and without an MDE.

Table 5: MDE Rate Calculation:

If a subject is early terminated from the study, the last day that the subject has been seen will be the duration in study, which can be the day of last follow-up, last imaging taken, an AE reported, or withdrawal from the study. If a subject is still in the study, the duration in study will be the time from index procedure to the cut off day that the database is locked or data snapshot is taken.

Subgroup analyses by-sex, by-race (based on subjects enrolled in the US only, since collection of race and ethnicity data may not be allowed outside the US as per local law and regulation), FreeFlo versus Closed Web configuration as proximal component, percutaneous access versus non-percutaneous, and by-region/study site will be performed on the primary study endpoint using descriptive statistics and reviewed for

Valiant Evo US Clinical Trial Statistical Analysis Plan

Version 2.0 Nov 1, 2017

This document is electronically controlled. Printed copies are considered uncontrolled.

clinical significant difference.

Secondary Endpoints

30-day Secondary Endpoint

The following secondary endpoints will be evaluated within 30 days post treatment:

- Peri-operative mortality
- All adverse events (AE) within 30 days including:
 - Major Adverse Event(s) (MAE)
 - Serious Adverse Event(s) (SAE)
- Secondary procedures
- Loss of stent graft patency at 30 day visit based on imaging findings
- Endoleaks at 30 day visit based on imaging findings

Detailed definitions of MAEs are defined in the Clinical Investigational Plan Appendix L.2.2. MAEs will be identified using codes in the Medical Dictionary for Regulatory Activities (MedDRA) provided by the Medtronic Clinical Safety group.

6-month Secondary Endpoints:

The following secondary endpoints will be evaluated:

- All-cause mortality within 183 days
- Aneurysm-Related Mortality within 183 days
- MDEs within 183 days

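### Safety data after withdrawal for safety or lack of effectiveness are sent outside the study, under a missing section F.7.6, with no stated route to the MDE count

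*Protocol*

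**What the plan says.** **Withdrawal.** Protocol F.7 (Subject accountability) sets a rule for discontinuation on safety or effectiveness grounds: further safety data are to be requested, but gathered outside the study, and leavers are not replaced. F.7.2 repeats the request and adds a pointer: "the subject shall be asked to be followed for collecting safety data outside the clinical study as further described in section F.7.6". In both the contents list and the body, section F.7 ends with "F.7.5 Medical care after study exit", which says: "After study exit the subjects will be followed as per routine standard of care by the investigational site or a treating physician". F.7.1 lists among the exit reasons: "Investigator requests that subject be withdrawn to protect the welfare of the subject".

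**Adjudication.** Protocol F.6.5 has the CEC adjudicate MDEs, unanticipated device effects, deaths and ruptures occurring during the conduct of the trial. SAP 7.9 says that all MDEs are adjudicated by the CEC.

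**Counting.** In SAP Table 5 the MDE rate is m/(m+k). The 30-day m is "No. of subjects who had at least one MDE with onset day from Day 0 to Day 30, inclusive". The 30-day k takes any subject in study for at least 1 day without an MDE; the 365-day k requires at least 305 days. The rule below the table reads: "If a subject is early terminated from the study, the last day that the subject has been seen will be the duration in study".

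**A contrasting rule.** Under Protocol F.2.2, treatment failures leave scheduled follow-up after 1 month, but their serious adverse events are still recorded in the eCRF for the whole trial.

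**The concern.** The device is a permanent implant, so withdrawal ends observation but not exposure. The protocol picks out the leavers whose reason for leaving may concern the device, asks them for further safety data, and places those data outside the study. The section meant to explain how does not exist, so a site cannot learn what to collect, for how long, or where to record it.

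The events that could be lost are the endpoint's own components: device-related secondary procedure, device-related death, conversion and aneurysm rupture. Consider a subject with successful deployment and an endoleak who is withdrawn on Day 20 and has a device-related secondary procedure on Day 27. If that procedure never reaches the eCRF and the CEC, Table 5 scores the subject as a 30-day success. With no rule written, whether to include such an event could also be decided after it is known, in a single-arm test whose result can turn on one event.

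**Working it through.** **1. How Table 5 treats a leaver whose later MDE is or is not recorded**

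| Withdrawal | MDE after withdrawal | Not recorded | Recorded and adjudicated |
|---|---|---|---|
| Day 1 to 29 | by Day 30 | in k (30-day success) | in m |
| Before Day 305 | by Day 365 | in neither m nor k at 1 year | in m at 1 year |
| Day 305 to 364 | by Day 365 | in k at 1 year | in m at 1 year |

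The definition of m has no in-study condition, so the right-hand column is permitted. What is missing is the step that gets the event into the database.

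**2. The plan's own power figures**

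Inputs are from Protocol C.7 and Table L-1, and SAP section 6: 30 days, n=87, goal 16%, expected rate 6%, one-sided 0.025; 1 year, n=63, goal 20%, expected rate 7.1%, one-sided 0.05. The test is exact binomial, with p = P(X ≤ x | n, goal).

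- 30 days: the largest passing count is 7. Power = P(X ≤ 7 | 87, 0.06) = 84.9%, against 85% stated.
- 1 year: the largest passing count is 7. Power = P(X ≤ 7 | 63, 0.071) = 92.3%, against 92% stated.

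**3. Sensitivity to one uncounted event**

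- 30 days: P(X ≤ 7 | 87, 0.16) = 0.0233, pass. P(X ≤ 8 | 87, 0.16) = 0.0495, fail.
- 1 year, withdrawn before Day 305: recovering the event adds the subject to numerator and denominator. P(X ≤ 7 | 63, 0.20) = 0.0473, pass. P(X ≤ 8 | 64, 0.20) = 0.0844, fail.
- 1 year, withdrawn from Day 305 on: recovery moves the subject from k to m. P(X ≤ 8 | 63, 0.20) = 0.0937, fail.

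The 30-day cut-off depends on n. With all 100 enrolled evaluable, P(X ≤ 8 | 100, 0.16) = 0.0147, so 8 passes; P(X ≤ 9 | 100, 0.16) = 0.0316, so 9 fails.

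**4. Chance of a wrong pass if w true events are left out**

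The number w is an assumption; the documents give no figure. At a true 30-day rate of 16% and n=87, P(pass) = P(X ≤ 7+w | 87, 0.16):

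| w | P(pass) |
|---|---|
| 0 | 2.3% |
| 1 | 5.0% |
| 2 | 9.3% |
| 3 | 15.8% |

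**5. Direction at 1 year**

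Take an observed 7/63 = 11.1% and one leaver before Day 305. If that leaver had an uncounted MDE, the rate including it is 8/64 = 12.5%, so the observed rate is too low. If the leaver stayed event-free, it is 7/64 = 10.9%, so the observed rate is too high. Both kinds are dropped, and the balance between them is unknown.

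**The case against.** The strongest reply is that this is a broken cross-reference plus one missing sentence. Much of it stands, and it rules out several stronger readings that a reader might infer.

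- **That these subjects cannot contribute an MDE.** Not supported. Table 5 sets m by onset day alone, so the use of such data is undefined, not prohibited. MDEs before withdrawal count, as do access and deployment failures. The handling may also be set out in the CEC charter, safety plan or data management plan, which are not available here.
- **That missing data are tied by rule to device failure.** Not supported. No rule withdraws a subject for device failure, and F.7 says that subjects should be encouraged to stay. That these leavers are the likeliest to have an MDE is plausible from the reason for leaving, but the documents do not show it.
- **That the bias can only be downward.** True of each uncounted event, but not of the 1-year rate overall (step 5).
- **That early migration would illustrate the 30-day loss.** It would not ordinarily do so: migration is judged against 1-month imaging. The endoleak example does not depend on that baseline.
- **That one lost event is likely to reverse a result.** Not shown. It matters only when the true count is one above the cut-off. At the planned rates that chance is P(X=8 | 87, 0.06) = 7.4% at 30 days and P(X=8 | 63, 0.071) = 4.4% at 1 year, before requiring that one of those events followed such a withdrawal.

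It is also fair to say that F.7.5 concerns medical care, not data capture.

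What the reply does not answer is that F.7 and F.7.2 state a rule, not just a gap: the data are placed outside the study, and no stated route brings them back. The tipping-point analysis in SAP 7.4 does not clearly fill the hole. It is optional, and a leaver whom Table 5 scores as a success may not be treated as missing.

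**Conclusion.** The concern holds in a limited form. Protocol F.7 and F.7.2 send requested safety data outside the study, F.7.2 relies on a section that does not exist, and neither document connects those data to the eCRF, the CEC or m. If they stay unconnected, Table 5 resolves the 30-day case in the device's favour and removes the subject from the 1-year rate when withdrawal falls before Day 305.

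Each uncounted post-withdrawal MDE lowers the observed rate. The size cannot be predicted, because the number of such withdrawals is not given and, for the 30-day test, only those before Day 30 matter. The p-values above show how thin the margin is at the planned minimum sizes of 87 and 63; they do not forecast a changed result. The change is worth making because the sponsor already asks for the data and the remedy is small.

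**What to change.** In F.7 and F.7.2, replace collection outside the study with collection inside it. With the subject's agreement, deaths, secondary procedures, conversions to open surgery and aneurysm ruptures after withdrawal are captured from records or by telephone, entered in the eCRF, sent to the CEC and counted in m by onset date. Only subjects who refuse further data collection stop contributing. State how long this capture continues. Remove the reference to F.7.6. Add a sentence under SAP Table 5 saying that adjudicated post-withdrawal events count in m.

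F.2.2 already keeps recording in the eCRF for treatment failures who leave scheduled visits, so the approach is not new to this protocol. The cost is protocol and SAP wording, a little site effort, and possibly a consent sentence. E.2.3 says that the consent form was revised for the 5-year extension, but its text was not available, so whether it already covers this cannot be checked. The sponsor should also accept that the resulting rate may be less favourable.

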IDE cohort will be followed up to 1-year and the primary endpoint will be tested against a 20% performance goal at 1 year for the post-approval analysis. Refer to Appendix L-6- PMA-S Post Approval analysis.

C.4 Study population

The study population will include those subjects who are appropriate candidates for endovascular repair of DTAA, and who meet the Inclusion/Exclusion criteria (defined in Section D).

C.5 Study design

The Valiant Evo US Clinical Trial is a prospective, multi-center, pre-market, non-randomized, single-arm trial. The trial is designed to assess the safety and effectiveness of the Valiant Evo Thoracic Stent Graft System in subjects with a descending thoracic aortic aneurysm (DTAA) who are candidates for endovascular repair.

The clinical performance of the Valiant Evo Thoracic Stent Graft will be evaluated in a total of 100 subjects with a hypothesis-based 30-day premarket composite safety and effectiveness endpoint.

The proposed primary composite safety and effectiveness endpoint is based on the proportion of subjects who experienced:

- (a) Access and/or deployment failures; and/or
- (b) Major Device Effect (MDE) within 30 days post index procedure

MDEs include the occurrence of any of the following:

- · Device-related secondary procedures
- Device-related mortality
- Conversion to open surgery
- Thoracic aortic aneurysm rupture

This primary composite endpoint will be compared to a PG of 16% MDE rate at 30 days.

All subjects included will continue to be followed under this investigational protocol beyond the 30-day primary endpoint out to 60 months post-implantation. Subjects will have required follow-up evaluations at the following time points:

- 1-month following the index procedure
- 6-months following the index procedure
- 12, 24, 36, 48 and 60-months following the index procedure

All subjects were consented for up to 2 years of follow-up. This was to accommodate any global clinical investigational requirements, if required. Subjects already enrolled and willing to extend

their follow-up from 12 to 60 months are to be re-consented. Enrolled subjects who decline to continue to participate in follow-up beyond 12-months shall exit the study upon the completion of their 12-month visit.

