1 Month (± 15 days)	15	30	45
6 Month (183 ±30 days)	153	183	213
12 Months (365 ±60 days)	305	365	425
24 Months (730 ±60 days)	670	730	790
36 Months (1095 ±60 days)	1035	1095	1155
48 Months (1460 ±60 days)	1400	1460	1520
60 Months (1825 ±60 days)	1765	1825	1885

Table F-1: Post-Implantation Follow-Up Visit Schedule and Windows

At all required follow-up visits subjects will undergo the following assessments and procedures:

- Physical Examination
- Chest CT/MRI with contrast
- EQ-5D questionnaire
- Adverse event assessment

A CT/MRI with contrast acquired at discharge (or before day 15) due to medical necessity may be used to meet the 1-month follow-up visit CT/MRI requirement if a CT/MRI with contrast cannot be obtained within the 1-month follow-up window due to the subject's health status based upon physician discretion.

If conversion to open repair is required during the follow-up period, then the subject will be followed for 30 days after the conversion, at which time the subject will be exited from the study.

F.3 Data collection requirements

Clinical data will be collected preoperatively to establish eligibility, at baseline, during the index procedure, throughout the hospital stay, and postoperatively at the required (and any interim imaging) follow-up visits described in Section F.2. The data collection schedule is summarized in Table F-2. Imaging source data will be sent to a Core Lab for analysis up to the 12-month follow-up visit. Any interim imaging of the stent graft region but not linked to a study visit should be recorded on the Interim Image eCRF (e.g. imaging performed as standard of care beyond the protocol required time points and/or when performed further to any issue observed at previous imaging Follow-up).

Imaging source data beyond 12-months post-index procedure will not be sent to the Core Lab for analysis. Instead, study sites are to report the results of the imaging performed as standard of care and in line with local and site requirements directly on the e-CRF. Routinely acquired images may be required for adjudication purposes in case of CEC adjudication or any other safety event.

Study data will be collected using electronic case report forms (eCRFs) as described in Section G.1. Clinical investigators must electronically review and approve all eCRFs. Medtronic monitors will perform source document verification of the eCRFs. The monitoring strategy will be defined in the monitoring plan.

Table F-2: Data Collection Schedule

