All endpoints will be analyzed descriptively. In general, qualitative parameters will be described by their distribution frequencies; quantitative parameters will be described by their mean, standard deviation, minimum, maximum, median, and number of subjects with assessable data.

The survival from all-cause mortality over one year time or longer will be described by the Kaplan-Meier survival curve and the associated Kaplan-Meier estimate will be calculated along with its standard error using the Greenwood method.

The primary study endpoint is a dichotomous study outcome; hence, an exact method based on the binomial distribution will be used for the hypothesis testing.

For events such as AEs, deaths and secondary procedures, that can occur or are observed at any time during the study, no time window will be applied. For such events, an event that occurs "within 1 month or 30 days" is an event that takes place between Days 0 to 30, inclusive. Similarly, an event that occurs "within 12 months or 365 days" is an event occurring between Day 0 to Day 365, inclusive. Date of event onset will be used to determine when the event occurred. Day 0 is referring to the day of index procedure.

For image-based assessments, such as stent-graft endoleak, patency, and other observations, the following time windows will be applied for by-visit data summaries:

Table H-1: Time Windows for Statistical Analyses

Study Visit	Target Day	Time Window
Implant	Day 0	Day 0

Study Visit	Target Day	Time Window
1 Month	Day 30	1 – 90 days
6 Months	Day 183	91 – 304 days
12 Months	Day 365	305 – 548 days
24 Months	Day 730	549 – 913 days
36 Months	Day 1095	914 – 1278 days
48 Months	Day 1460	1279 –1643 days
60 Months	Day 1825	1644 – 2009 days

If there are two or more assessments in the same time window, unless otherwise specified, the assessment closest to the target day will be used in the analysis of event rate at a given time point.

In addition to endpoints, summaries of subject disposition, demographics, baseline characteristics, and subject accountability will be provided.

During statistical analysis, imputation of missing data will not be performed except for data related to the onset date of an adverse event or a death. In cases where the onset date of an event or a death is incomplete and unresolvable via data query, the 15th day of the known month or July 1st of the known year will be used.

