Thank you for completing the Explant Forms and returning the device. Medtronic uses this information to meet FDA requirements and track product performance.

EXPLANT PROCEDURE OBSERVATION FORM

PATIENT INFORMATION	
Patient IDE/ Study ID	
Name:	
DOB (Month/Day/Year):/	
IMPLANT INFORMATION	
Date of Implant:/	
Implanting Physician:	
Implanting Hospital Name:	
City and State:	
Country:	
EXPLANT INFORMATION Date of Explant/Autopsy://	
Explanting Dhysician:	
Explanting Physician:	
Name of Hospital:	
Address:	
City and State:	
Country:	
Telephone: ()	
REASON FOR EXPLANT	
REASON FOR EAFLANT	
☐ Planned Surgical Conversion	
☐ Emergent Conversion	
☐ Autopsy Date of Death:/	
Remarks about procedure:	

Medtronic

Evidence of inflammation	\square Yes \square No	
Comments: Thrombosis present in the sealzones		
Comments:Calcification present in the sealzones		
Comments:		
How well was the device attached to the p	patient's tissue?	
Proximally : □ Comes out easily from ao	ortic vessel	
☐ Appears firmly attached t	o aortic vessel	
Mid body: ☐ Comes out easily from an	neurysm contents	
☐ Appears firmly attached t	o aneurysm contents	
Distally (L) : □ Comes out easily from ili	ac/aortic vessel	
☐ Appears firmly attached t	o iliac/aortic vessel	
Distally (R) : □ Comes out easily from ili	ac/aortic vessel	
☐ Appears firmly attached t	o iliac/aortic vessel	
Comments		
Successful Surgical Conversion: Yes		

EXPLANTED DEVICE INFORMATION

DEVICE	CATALOG NUMBER	LOT NUMBER
Bifurcated Body		
□ Distal Left		
□ Distal Right		
Contralateral Limb		
Iliac Extension		
□ Left		
□ Right		
Iliac Extension		
□ Left		
☐ Right Iliac Extension		
□ Right		
Aortic Cuff		
7 tortio our		
AUI		
□ Distal Left		
□ Distal Right		
Thoracic, Proximal Main		
Thoracic, Distal Main		
Thoracic, Distal Main		
Thoracic, Proximal Extension		
Thoracic, Distal Extension		
Other (Specify)		
	Additional Comments	
		_
Form completed by:		
Title:		
Date:		

L.5 Informed Consent Template

L.6 Post PMA-S approval Analysis

Following PMA-S approval, the postmarket evaluation will be conducted and results provided to the FDA once the last subject in the study completes the 12-month follow-up visit.

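### The 1-year MDE endpoint runs to Day 365, but a US subject who declines the extension can exit from Day 305 and still be counted event-free for the full year

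*Protocol*

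**What the plan says.** **Event window.** Protocol H.1 applies no visit window to deaths, AEs and secondary procedures; an event within 12 months "is an event occurring between Day 0 to Day 365, inclusive". The 365-day numerator in SAP 7.9, Table 5 matches: "No. of subjects who had at least one MDE with onset day from Day 0 to Day 365, inclusive".

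**Visit window.** Protocol Table F-1 lists "12 Months (365 ±60 days", that is, Day 305 to Day 425. Section F.2.4 requires a contrast CT or MRI at the visit.

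**Exit rule.** Protocol C.5: "Enrolled subjects who decline to continue to participate in follow-up beyond 12-months shall exit the study upon the completion of their 12-month visit". Under F.7.5, care after exit is routine care. I found no later status contact for these subjects.

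**Event-free count.** The 365-day denominator in SAP Table 5 adds "No. of subjects who have been in study for at least 305 days and without an MDE". On duration, SAP 7.9 says: "If a subject is early terminated from the study, the last day that the subject has been seen will be the duration in study".

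**A conflicting rule.** SAP section 5 has subjects followed until the last enrolled subject's 1-year visit or US PMA approval, whichever comes later. That does not agree with C.5. SAP section 3 names the protocol as the primary resource for clarification.

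**Use of the result.** Protocol C.3 and Appendix L.6 test the 1-year rate against 20%. The evaluation follows "once the last subject in the study completes the 12-month follow-up visit".

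**The concern.** The numerator needs observation to Day 365, but the event-free count accepts 305 days. For most subjects still in the study this does little harm, because events after an early visit are still collected. For a decliner, C.5 ends collection on the visit day.

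Take a decliner scanned on Day 310, with a graft problem found and treated on Day 330. If the CEC judges the procedure device-related, it is an MDE inside the 365-day window. The subject left on Day 310, so the event does not reach the numerator, while the 310 days in study put the subject in the denominator as a success. The plan can be followed exactly and still give this result.

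The timing is unhelpful because the 12-month scan is itself a likely trigger for reintervention, and device-related secondary procedures are an MDE component. SAP 7.9 applies the Table 5 calculation to other non-image events through 1 year (mortality, secondary procedures, MAEs, SAEs, conversion, rupture), so those proportions share the gap.

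**Working it through.** **1. Reproduce the plan's 1-year figure.** Inputs from Protocol Table L-1 and SAP Table 2: N = 63, goal 20%, assumed rate 7.1%, one-sided exact binomial test at 0.05.

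- P(X ≤ 7 | 63, 0.20) = 0.047, a pass.
- P(X ≤ 8 | 63, 0.20) = 0.094, a fail.
- Power = P(X ≤ 7 | 63, 0.071) = 0.923, against 92% stated. The figure reproduces.

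The pass mark is therefore 7 events of 63.

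**2. Length of the gap.** Earliest exit is Day 305 and the window ends on Day 365: 365 − 305 = 60 days. Only decliners seen before Day 365 are affected. After a later visit, a new procedure falls outside the endpoint by definition.

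**3. Share of scan-prompted procedures lost.** The documents give no visit distribution and no lag from scan to procedure. Assume visits uniform over Day 305 to 425 (120 days) and a lag L uniform over 7 to 45 days (mean 26). A procedure is lost if it falls after exit and on or before Day 365:

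- P(visit + L ≤ 365) = E[(60 − L)/120] = (60 − 26)/120 = 0.283.

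Day 365 is the target, so visits may cluster there. With the same lag:

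- Triangular on Day 305 to 425, peak at Day 365: E[(60 − L)²/7200] = (53³ − 15³)/(3 × 38 × 7200) = 0.177.
- Normal, centred on Day 365 with SD 15 days: E[Φ(−L/15)] = 0.082.

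**4. Expected lost events at 63 evaluable.** Assume that 20% to 40% decline and that 2% to 5% of 12-month scans prompt a procedure counted as an MDE. Lost events = 63 × decline share × procedure share × lost share.

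| Visit timing | Low (20%, 2%) | High (40%, 5%) |
|---|---|---|
| Uniform (0.283) | 63 × 0.20 × 0.02 × 0.283 = 0.07 | 63 × 0.40 × 0.05 × 0.283 = 0.36 |
| Triangular (0.177) | 0.04 | 0.22 |
| Normal, SD 15 (0.082) | 0.02 | 0.10 |

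For uniform visits, the chance of losing at least one event is 1 − (1 − 0.00113)⁶³ = 7% to 1 − (1 − 0.00567)⁶³ = 30%.

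**5. Effect on the test.** At a true rate of 20%, the observable rate is 0.20 minus the lost proportion.

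- Uniform, low: 0.20 − 0.0011 = 0.1989; P(X ≤ 7 | 63) = 0.049.
- Uniform, high: 0.20 − 0.0057 = 0.1943; P(X ≤ 7 | 63) = 0.059.
- Triangular: 0.049 to 0.054. Normal: 0.048 to 0.050.
- No loss: 0.047.

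**6. Power if unreached subjects are dropped.** Repeating step 1 at 7.1% with fewer evaluable subjects:

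- 5 removed (N = 58, pass at 6 events): 0.884.
- 10 removed (N = 53, pass at 5 events): 0.828.

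**The case against.** **SAP section 5 may keep subjects under observation.** Under its follow-up rule, most early-visit subjects would be observed past Day 365. But it contradicts C.5, the SAP defers to the protocol, and it does not guarantee Day 365 for every subject. It makes the point partly a conflict to reconcile; it does not close the gap.

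**Mortality has another analysis.** H.1 and SAP 7.10 plan Kaplan-Meier estimates, which censor at exit. This stands: only the Table 5 mortality proportion is exposed.

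**Table 5 also has an opposing bias.** It keeps every subject with an MDE by Day 365 and drops event-free subjects with under 305 days, which raises the rate. With as few as 63 evaluable of 100 enrolled, that could be the larger effect. This stands. A reader might infer that the reported 1-year rate is too low overall; the documents support that direction for this mechanism only.

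**Half the data may fall under another protocol.** C.7 allows up to 50% of subject data from the International trial, whose protocol is not among these documents. The two are stated to be identical on eligibility criteria; nothing is said about exit. The finding is therefore limited to US subjects.

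**L.6 sets no data cut.** A reader might infer that it locks the data before the last subject's Day 365. It says when the evaluation is conducted and reported, and at most a few late subjects could be affected.

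**The missing-data plan may cover it.** The tipping-point analysis in SAP 7.4 is optional and addresses missing outcomes. These subjects are classed as event-free, so it would not reach them. This objection fails.

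**Conclusion.** The gap is real. Read together, C.5, Table F-1, H.1 and SAP Table 5 allow a true MDE before Day 365 to be scored as a success, and this mechanism works in one direction only. It concerns the 1-year post-approval test and the Table 5 proportions for other non-image 365-day events.

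The expected size is modest: under uniform visits, 0.07 to 0.36 lost events at 63 evaluable and a false-pass probability of 4.9% to 5.9% against 4.7%, and less if visits cluster near Day 365. Decline share, procedure share, lag and visit timing are all assumed. One lost event changes the decision only at the boundary, where 8 true events would be recorded as 7.

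A reader might infer a larger inflation, such as 6.5%. That requires a quarter of subjects to exit on Day 305 itself, with 60/365 = 16.4% of all 1-year events falling after that day; nothing in the documents supports so extreme a pattern. A reader might also infer that the 30-day primary result is affected. It is not, because the exit rule operates only at the 12-month visit.

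**What to change.** 1. **Protocol C.5:** state that a subject who declines the extension exits at the later of the 12-month visit and Day 365, with a documented phone or record check on or after Day 365 for death, MDE, secondary procedure and SAE.
2. **SAP section 5:** reconcile the follow-up sentence with C.5.
3. **International protocol:** confirm a matching exit rule and consent. C.5 says subjects consented to up to 2 years, but that covers the US trial only.
4. **Appendix L.6:** take the 1-year data cut after the last subject passes Day 365.
5. **SAP Table 5:** keep the main denominator. Add a sensitivity analysis that treats event-free subjects who exited before Day 365 without a completed check as missing, both by exclusion and by tipping point.

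**Cost:** one call or chart check per early-visit decliner and a data cut up to 60 days later. Where the check is completed, N and power are unchanged. The exclusion analysis loses power if subjects cannot be reached: from 0.923 to 0.884 with 5 of 63 unreached, or 0.828 with 10. That is why it should be a sensitivity analysis and not the main one.
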